5.1 Inclusion Criteria

In order to be eligible to participate in this study, an individual must meet all of the following criteria:

CONFIDENTIAL

This material is the property of the NYU School of Medicine and Langone Medical Center. Do not disclose or use except as authorized in writing by the study sponsor
Interventional Template Version: 28 APR 2017

1. Listed for heart transplant at NYU Langone Health (including candidates listed for dual organs)
2. Able to travel to the NYU Langone Health for routine post-transplant visits and study visits for a minimum of 6 months after transplantation
3. No active illicit substance abuse
4. Weight at least 50kg
5. Women of childbearing potential must agree to use birth control in accordance with Mycophenolate Risk Evaluation and Mitigation Strategy (REMS) after transplant due to the increased risk of birth defects and/or miscarriage
6. Both men and women must agree to use at least one barrier method after transplant to prevent any secretion exchange
7. Able and willing to provide informed consent
8. Age 18 years old and older

Furthermore, the deceased donors from whom the organs will be procured must meet the following criteria:

1. Detectable HCV RNA by nucleic acid test (NAT) or positive anti-HCV antibody
2. Donor heart meets standard NYU Langone Health clinical criteria for procurement

5.2 Exclusion Criteria

An individual who meets any of the following criteria will be excluded from participation in this study:

1. HIV positive
2. HCV RNA positive or history of previously treated HCV
3. Evidence of active Hepatitis B infection or on active antiviral treatment for HBV
4. Pregnant or nursing (lactating) women
5. Use of strong CYP3A inducers

Furthermore, the deceased donors from whom the organs will be procured will be excluded if they meet any of the following criteria:

1. Confirmed HIV positive
2. Evidence of active HBV infection
3. Known previously failed treatment for HCV

5.3 Vulnerable Subjects

Vulnerable subjects will not be eligible for enrollment.

5.4 Strategies for Recruitment and Retention

Recruitment of patients will occur during routine evaluation visits to determine candidacy for a heart transplant at NYU Langone Health. Patients will be informed of the option to enroll in this study, and if interested, detailed information pertaining to the risks and benefits of the trial will be provided.

The signing of the acknowledgment to consider participation in the study will occur in the outpatient clinic. No additional information about potential candidates will be collected to determine interest or candidacy for this trial than would otherwise be normally collected as per standard of care for evaluation for a heart transplant.

Written informed consent for actual enrollment in the study will occur in the inpatient setting once a viable organ offer has been identified and the patient is admitted for potential transplantation.

The target sample size will be 20 patients.

CONFIDENTIAL

This material is the property of the NYU School of Medicine and Langone Medical Center. Do not disclose or use except as authorized in writing by the study sponsor
Interventional Template Version: 28 APR 2017

5.4.1 Use of DataCore/Epic Information for Recruitment Purposes

This study may utilize EPIC to identify subjects.

Any recruitment information sent by email will utilize Send Safe email.

Potential subjects will already be known to the study team as they will be under their care as candidates and/or waitlist registrants for heart transplant. The study team will conduct an in person consultation with the patients to explain the study as well as discuss the risks, benefits, and alternatives

Approved recruitment language will be used to communicate the reason they are being contacted and subjects will be asked if they are interested in participating in this specific study. Should the potential subjects agree, the study team will provide the subjects with information regarding the next steps for participation.

If a subject requests information regarding opting out of further recruitment for all research, subjects will be directed to contact [contact] or [name].

5.5 Duration of Study Participation

Duration of participation is expected to be 12 months.

5.6 Total Number of Participants and Sites

20 patients are expected to be enrolled and transplanted. No sites outside of NYULMC will enroll patients.

5.7 Participant Withdrawal or Termination

5.7.1 Reasons for Withdrawal or Termination

Participants are free to withdraw from participation in the study at any time upon request. An investigator may terminate participation in the study if:

- Any clinical adverse event (AE), laboratory abnormality, or other medical condition or situation occurs such that continued participation in the study would not be in the best interest of the participant
- The participant meets an exclusion criterion (either newly developed or not previously recognized) that precludes further study participation

5.7.2 Handling of Participant Withdrawals or Termination

Discontinuation of the study agent is not anticipated as this will place patients at risk to develop acute or chronic HCV. For patients who do elect to discontinue the study agent Mavyret due to intolerance or SAEs/AEs, the following steps will be taken:

Hepatology consultation to guide management, which could include:

Continued surveillance for evidence of HCV viremia in patients who had cleared their viremia
Conversion to an alternate HCV treatment that is able to be tolerated by the patient

5.8 Premature Termination or Suspension of Study

This study may be temporarily suspended or prematurely terminated if there is sufficient reasonable cause. Written notification, documenting the reason for study suspension or termination, will be provided by the suspending or terminating party to the Principal Investigator. If the study is prematurely terminated or suspended, the PI will promptly inform the IRB and will provide the reason(s) for the termination or suspension.

Circumstances that may warrant termination or suspension include, but are not limited to:

- Determination of unexpected, significant, or unacceptable risk to participants
- Demonstration of efficacy that would warrant stopping

CONFIDENTIAL

This material is the property of the NYU School of Medicine and Langone Medical Center. Do not disclose or use except as authorized in writing by the study sponsor

- Insufficient compliance to protocol requirements
- Data that are not sufficiently complete and/or evaluable
- Determination of futility

Study may resume once concerns about safety, protocol compliance, data quality is addressed and satisfy the IRB and DSMB.

6 Study Agent

6.1 Study Agent(s) and Control Description

Mavyret is available in tablet form. The single tablet contains two active agents: glecaprevir (100nmg) and pibrentasvir (40mg).

No IND is required here as this is an FDA-approved agent for the treatment of HCV infection. The drug is marketed and will be available through the pharmacy. In accordance with FDA Guidelines, we attest that this study meets all of the following exemption criteria and that no IND is required:

- Mavyret is lawfully marketed in the United States
- This investigation is not intended to be reported to the FDA in support of a new indication for Mavyret
- This investigation is not intended to support a change in marketing for Mavyret
- This investigation does not involve a route of administration, dosing change, or patient population change compared to what is FDA-approved for Mavyret
- This investigation will be conducted in compliance with the NYULMC IRB review and consenting requirements
- This investigation is not intended to promote or commercialize the product Mavyret.

Detailed documentation of the above FDA Guidelines is also uploaded as an attachment in Research Navigator.

6.1.1 Acquisition

These agents are FDA approved and will be obtained from the NYULMC pharmacy via standard procedure for medication ordering.

6.1.2 Formulation, Appearance, Packaging, and Labeling

This is an open label study and the drug will appear as it provided directly from the manufacturer. The tablets are pink, oblong-shaped, film-coated, and debossed with "NXT" on one side. The drug will be packed in the standard manufacturer's packing and all standard and package inserts will be retained.

6.1.3 Product Storage and Stability

Mavyret is dispensed from the manufacturer in a 4-week (monthly) or an 8-week carton. Each weekly carton contains seven daily dose wallets. Each monthly carton contains four weekly cartons. Each 8-week carton contains 2 monthly cartons. Each child resistant daily dose wallet contains three 100 mg/40 mg glecaprevir/pibrentasvir tablets. Storage is at room temperature.

6.1.4 Preparation

The drug is a tablet for oral ingestion. No preparation is required.

6.1.5 Dosing and Administration

The dose will be three tablets taken at one time, once daily with a meal. The standard duration of therapy is daily administration for 8-weeks.

CONFIDENTIAL

This material is the property of the NYU School of Medicine and Langone Medical Center. Do not disclose or use except as authorized in writing by the study sponsor
Interventional Template Version: 28 APR 2017

6.1.6 Route of Administration

Oral

6.1.7 Dose Adjustments/Modifications/Delays

No dose adjustments are anticipated. Subjects will be counseled as to the importance of strict adherence to the medication regimen. Subjects will be advised to notify the study team of any missed or delayed doses. If a dose is missed and less than 18 hours have elapsed since the scheduled time, patients will be instructed to take the missed dose with the next meal and resume the regular schedule the following day. If a dose is missed and more than 18 hours have elapsed since the scheduled time, then the patients will be instructed not to take the missed dose, but to resume the regular schedule the next day.

6.1.8 Duration of Therapy

The duration of therapy will be 8-weeks.

6.1.9 Tracking of Dose

While in the hospital, any doses will be given by nursing staff and accountability will be maintained in the electronic medical record. Once outpatient, patients will attend regularly scheduled clinic appointments for routine care following a heart transplant and medication review will occur on each of these visits to ensure that the medication is being taken properly. Laboratory testing for HCV will be performed as described. Clearance of HCV and SVR will serve as clinical evidence that the medication is being taken properly.

6.2 Study Agent Accountability Procedures

For therapy that is initiated during the inpatient hospitalization post-transplant, the NYU Langone pharmacy will dispense the medication and it will be given to the patient by the bedside nurse. For outpatient therapy the drug will be distributed to the study subjects together with the standard of care medications they will require after a heart transplant. The drug is supplied in either 4-week or 8-week batches. Completion of the course will leave no remaining doses. All the supplied product will be used.

7 Study Procedures and Schedule

7.1 Study Procedures/Evaluations

7.1.1 Study Specific Procedures

Note that the medical history and medication history that pertains to candidacy for heart transplantation are considered standard of care procedures and evaluations for heart transplantation, and are not considered here. Patients are not considered candidates for this trial if there is any contraindication to their standard candidacy for a heart transplant. As such, procedures and evaluations specific to participation in this study include:

- Medical history to assess for any history of acute or chronic liver disease, and any prior infection with HCV, HBV, or HIV
- Medication history to assess for any potential interacting drugs including (amiodarone, statins, anti-epileptics, hormonal contraceptives, antipsychotics, recreational drugs, immunosuppressant drugs)
- Physical examination (height, weight, baseline blood pressure, heart rate, oxygen saturation, assess for absence of jaundice/scleral icterus, abdominal examination to assess for absence of hepatosplenomegaly, ascites, abdominal wall varices)
- Laboratory evaluations. Serum evaluation for HCV and HBV NAT testing. Serum evaluation for HCV HBV and HIV serologies, described in detail below.

CONFIDENTIAL

This material is the property of the NYU School of Medicine and Langone Medical Center. Do not disclose or use except as authorized in writing by the study sponsor

- A discussion of if the results of any positive blood tests for HCV infection, and discussions of response to treatment once treatment has begun.

7.1.2 Standard of Care Study Procedures

Heart transplantation and all associated procedures will be considered standard of care including: the transplant procedure itself and requisite intra-operative procedures and hemodynamic monitoring, post-operative ICU-level care, inpatient hospital unit care, outpatient post-operative care including, standard induction and maintenance immunosuppression, and standard post-transplant anti-infectious prophylaxis (anti-fungal, anti-pneumocystis, and anti-CMV prophylaxis).

7.2 Laboratory Procedures/Evaluations

7.2.1 Clinical Laboratory Evaluations

The following tests will be reviewed and recorded for patients who are included in the study but will be performed as standard of care for heart transplant recipients:

- **Hematology:** hemoglobin, hematocrit, white blood cells (WBC) with differential count, platelet count
- **Biochemistry:** sodium, potassium, CO₂, BUN, creatinine, total bilirubin, alanine aminotransferase (ALT), aspartate aminotransferase (AST), alkaline phosphatase
- **Coagulation:** INR
- **Pregnancy test**, usually to be done within 24 hours prior to study intervention and results must be available prior to administration of study product.
- **HBV NAT testing:** PCR test for detection and quantification of HBV viral load, an indicator of active HBV infection. These tests are performed as standard of care for patients who receive transplanted organs from a donor who is designated "PHS increased infectious risk." By definition, all HCV positive organ donors meet criteria for designation as PHS increased infectious risk.
- **HBV serologic testing (HBsAb, HBsAg, HBcoreAb):** serologic testing to evaluate for the presence of immunity to HBV or the evidence of prior infection with HBV. These tests are performed as standard of care for patients who receive transplanted organs from a donor who is designated "PHS increased infectious risk." By definition, all HCV positive organ donors meet criteria for designation as PHS increased infectious risk.
- **HIV serologic testing (HIV1 and 2 antigen/antibody 4th gen):** serologic testing to evaluate for the presence of HIV infection. These tests are performed as standard of care for patients who receive transplanted organs from a donor who is designated "PHS increased infectious risk." By definition, all HCV positive organ donors meet criteria for designation as PHS increased infectious risk.

The following tests will be performed specifically for purposes of this study:

- **HCV genotyping:** [REDACTED]

Hepatitis C Viral RNA, Genotype, LiPA® [REDACTED]

Recipient testing for HCV genotyping will be ordered by standard ordering procedures through Epic as with all other tests.

- **HCV NAT testing:** PCR test for detection and quantification of HCV viral load
- **HCV serologic testing:** serologic evaluation for the presence of anti-HCV antibodies

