Participant Duration	One year
Duration of IP administration	Eight weeks
Population	Adult patients active on the UNOS waiting list for a heart transplant
Study Sites	Single center (NYU Langone Hospital)
Number of participants	Ten patients
Description of Study Agent/Procedure	The heart transplantation will be performed per standard of care techniques, and all post-transplant management of the transplanted organ, including immunosuppression, will be carried out per standard of care. The study-specific interventions will be surveillance for the development of hepatitis C viremia post-transplant, the treatment of viremia with an FDA-approved drug, and then surveillance for sustained virologic response post-treatment.
Reference Therapy	Not applicable
Key Procedures	Monitoring for transmission of hepatitis C after heart transplant, treatment of viremia if it develops, and monitoring for response to treatment.
Statistical Analysis	In this small pilot study, descriptive statistics will be used.

CONFIDENTIAL

This material is the property of the NYU School of Medicine and Langone Medical Center. Do not disclose or use except as authorized in writing by the study sponsor

Interventional Template Version: 05 JAN 2017

Schematic of Study Design

CONFIDENTIAL

This material is the property of the NYU School of Medicine and Langone Medical Center. Do not disclose or use except as authorized in writing by the study sponsor
Interventional Template Version: 28 APR 2017

1 Key Roles

Principal Investigator

[name]
Associate Professor of Medicine
Clinical Director, Heart Failure Program
Medical Director, Heart Transplant and Ventricular Assist Device Program
The Leon H. Charney Division of Cardiology, NYU Langone Health
[name]
[REDACTED]
[REDACTED]

Co-Investigators:

[name]
Professor of Surgery
Surgical Director, Heart Transplantation and Mechanical Circulatory Support
NYU Langone Cardiothoracic Surgery Associates
[name]
[name]
[REDACTED]
[REDACTED]

[name] PhD
Assistant Professor of Surgery
Vice Chair for Research, NYU Langone Transplant Institute
[name],
[name]
[REDACTED]
[REDACTED]

[name]
Professor of Medicine
Director, Hepatology
NYU Langone Hepatology Associates
[name]
[name]
[REDACTED]
[REDACTED]

[name]
Associate Director of VAD and Heart Transplant
NYU Langone Cardiothoracic Surgery Associates
[name]

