In this pilot study we propose utilizing HCV positive donors for HCV negative patients on the waiting list for a heart transplant at NYU Langone. We will propose careful early post-transplant surveillance for the development of HCV viremia. We anticipate that approximately one-third of the patients will not develop viremia, despite the donor designation HCV positive. We anticipate that two-thirds of patients will develop early post-transplant HCV viremia. These patients will be immediately treated with an FDA-approved anti-HCV therapy which we expect will cure the HCV.

Willingness to participate in this trial will afford patients quicker access to heart transplantation, and will have the potential to reduce waitlist mortality.

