7.3.2 Enrollment/Baseline

Enrollment/Baseline Visit (Day -1 to 0)

CONFIDENTIAL

This material is the property of the NYU School of Medicine and Langone Medical Center. Do not disclose or use except as authorized in writing by the study sponsor
Interventional Template Version: 28 APR 2017

- Organ offer for a HCV-positive donor heart is received. The donor inclusion criteria are reviewed to ensure all donor criteria are met.
- The organ offer and the opportunity to participate in the trial are discussed with the patient and if the patient accepts, the patient is then admitted to the hospital in preparation for heart transplant.
- Inclusion/exclusion criteria for the recipient are reviewed again
- Written informed consent to participate in the trial is obtained.
- Obtain urine pregnancy test from any woman participant of childbearing age.
- Record vital signs, results of examinations, other assessments.
- Collect blood for baseline hematology, biochemistry coagulation, HCV NAT and serologies, HBV NAT and serologies, and HIV serology.
- Heart transplant operation is performed as per standard of care techniques.
- Donor blood is acquired with the donor organ, and donor serum sent to Quest Laboratories for HCV genotyping (to be performed in parallel with the transplant). Donor serum is banked for repeat testing in the event of indeterminate genotyping results.

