- In person visit, record vital signs
- Record standard of care labs: hematology, biochemistry, coagulation, HBV serologies and NAT, HIV serologies
- Collect study labs: HCV NAT and serology

POW16 (+/- 7 days)

- Record standard of care labs: hematology, biochemistry, coagulation
- Collect study labs: HCV NAT and serology

POW20 (+/- 7 days)

- Record standard of care labs: hematology, biochemistry, coagulation
- Collect study labs: HCV NAT and serology

POW24 (+/- 14 days): INTERIM ASSESSMENT AT 6-months post-transplant

- In person visit, record vital signs
- Record standard of care labs: hematology, biochemistry, coagulation
- Collect study labs: HCV NAT and serology

MAVYRET TREATMENT ARM SCHEDULE OF EVENTS

PMW0 (+/- 5 days of determination of HCV viremia)

- Initiate Mavyret therapy (daily dosing x 8 weeks)
- In person visit, record vital signs

PMW1 (+/- 1 day)

- Record standard of care labs: hematology, biochemistry, coagulation
- Collect study labs: HCV NAT and serology

PMW2 (+/- 2 day)

- Record standard of care labs: hematology, biochemistry, coagulation
- Collect study labs: HCV NAT and serology

PMW3 (+/- 3 day)

- Record standard of care labs: hematology, biochemistry, coagulation

CONFIDENTIAL

This material is the property of the NYU School of Medicine and Langone Medical Center. Do not disclose or use except as authorized in writing by the study sponsor
Interventional Template Version: 28 APR 2017

- Collect study labs: HCV NAT and serology

PMW4 (+/- 5 day)

- In person visit, record vital signs
- Record standard of care labs: hematology, biochemistry, coagulation, HBV serologies and NAT, HIV serologies
- Collect study labs: HCV NAT and serology

PMW5 (+/- 5 day)

- Record standard of care labs: hematology, biochemistry, coagulation
- Collect study labs: HCV NAT and serology

PMW6 (+/- 5 day)

- Record standard of care labs: hematology, biochemistry, coagulation
- Collect study labs: HCV NAT and serology

PMW7 (+/- 5 day)

- Record standard of care labs: hematology, biochemistry, coagulation
- Collect study labs: HCV NAT and serology

PMW8 (+/- 5 day)

- In person visit, record vital signs
- Confirm completion of Mavyret treatment course
- Record standard of care labs: hematology, biochemistry, coagulation
- Collect study labs: HCV NAT and serology

PMW9 (+/- 5 day)

- Record standard of care labs: hematology, biochemistry, coagulation
- Collect study labs: HCV NAT and serology

PMW10 (+/- 5 day)

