By signing this form, I acknowledge that I have been informed that participation in the above study may be an option for me. The potential risks and benefits of this study have been explained to me and I have received a copy of the HCV Heart Research Study Fact Sheet.

Signing this form does not guarantee that I will be enrolled in this study.

Signing this form does not mean that I cannot receive a heart transplant at NYU Langone outside of this study.

Signing this form designates that if a suitable organ offer from an HCV positive heart donor becomes available, I would like to be contacted and offered enrollment in the study.

Name of Patient (Print) _____ Signature of Patient _____ Date _____

Name of Person Providing this Form (Print) _____ Signature of Person Providing this Form _____ Date _____

CONFIDENTIAL

This material is the property of the NYU School of Medicine and Langone Medical Center. Do not disclose or use except as authorized in writing by the study sponsor
Interventional Template Version: 28 APR 2017

20 Schedule of Events

For patients who do not develop HCV viremia during the surveillance phase, the following schedule will apply for the entire course of the study:

Activity	Screening visit (Day -365 to -1)	Enrollment visit (Day -1 to 0)	SURVEILLANCE PHASE			
			POW1 (+/- 1 day)	POW2 (+/- 2 day)	POW3 (+/- 3 day)	POW4 (+/- 5 day)
Study team procedures						
Acknowledgement of willingness to participate, provision of Study Fact Sheet	X					
Medical History	X					
Physical Exam	X	X	X	X		
Height	X	X	X	X		X
Weight	X	X	X	X		X
Vitals signs	X	X	X	X		X
Review all donor and recipient inclusion/exclusion criteria		X				
Signing of informed consent		X				
Study specific interventions						
Heart transplant operation		X				
Initiate Mavyret treatment						
Study specific laboratory tests						
Donor serum HCV genotyping		X				
Recipient serum HCV genotyping						
HCV NAT (PCR)	X	X	X	X	X	X
HCV serology (HCV Ab)	X	X				
SOC laboratory tests						
Biochemistry (Na, K, CO2, BUN, Cr, total bili, AST, ALT, alk phos)	X	X	X	X	X	X
Hematology (WBC with ANC, HGB, PLT)	X	X	X	X	X	X
Coagulation (INR)	X	X	X	X	X	X
Urine pregnancy test		X				
HBV NAT (PCR)	X	X				
HBV serology (HBsAb, HBsAg, HBcoreAb)	X	X				
HIV serology (HIV1/2 antigen/antibody 4 th gen)	X	X				

CONFIDENTIAL

This material is the property of the NYU School of Medicine and Langone Medical Center. Do not disclose or use except as authorized in writing by the study sponsor

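### No pregnancy test is scheduled at PMW0, so a site following the schedule could start Mavyret on a result at least 6 days old; add one at PMW0.

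*Protocol*

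**What the plan says.** - **Timing rule.** Protocol Section 7.2.1 describes the pregnancy test as "usually to be done within 24 hours prior to study intervention and results must be available prior to administration of study product". It groups the test with those that "will be performed as standard of care for heart transplant recipients".
- **The one scheduled test.** Section 7.3.2 (Day -1 to 0) reads "Obtain urine pregnancy test from any woman participant of childbearing age". The Section 20 table marks the test in the enrollment column only.
- **Start of the drug.** Section 7.3.3 gives the visit as "PMW0 (+/- 5 days of determination of HCV viremia" and its first item as "Initiate Mavyret therapy (daily dosing x 8 weeks". The other item is an in-person visit with vital signs. The PMW0 column in Section 20 adds physical exam, height, weight and recipient genotyping. Its pregnancy-test row is blank, as it is at every later visit.
- **What counts as the intervention.** The Protocol Summary says "The study-specific interventions will be surveillance for the development of hepatitis C viremia post-transplant, the treatment of viremia with an FDA-approved drug", and it treats the transplant as standard of care. The Section 20 table lists both the transplant and the start of Mavyret as study-specific interventions.
- **Expected timing of viremia.** Section 2.1 says "We anticipate that two-thirds of patients will develop early post-transplant HCV viremia".

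**The concern.** The test is placed before the transplant, but the study product is given days to weeks later. Three provisions depend on knowing pregnancy status at that point:

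- Section 5.2 excludes pregnant women.
- Section 5.7.1 lets the investigator end participation when an exclusion newly develops, but no test scheduled after Day 0 would detect a pregnancy.
- Section 8.4.4 says there are no Mavyret data in pregnancy and plans counselling on whether to continue or stop the drug. Without a test at PMW0, that discussion could come only after dosing has begun.

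At stake is the safety of a small number of women. The SVR endpoint and its analysis do not depend on this.

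**Working it through.** The plan gives no figure for the age of the result, so there is none to reproduce. The age follows from the visit schedule.

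**Inputs**
- Test day: -1 to 0 (Section 7.3.2).
- HCV NAT days in surveillance: 7 × week, with windows of ±1, ±2 and ±3 days at POW1, POW2 and POW3, and ±5 days from POW4 to POW8 (Section 7.3.3).
- Lag from determination of viremia to PMW0: 0 to 5 days. Taken literally, the ± would also allow a start before viremia is determined. Treatment requires detected viremia, so only the positive side applies.
- Assumption: the NAT result is available the same day. A slower result makes every age longer.

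**Formulas**
- Youngest result = earliest NAT day − 0.
- Oldest result = latest NAT day + 5 + 1 (test on Day -1, start 5 days after determination).

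| Viremia found at | NAT day | Youngest (days) | Oldest (days) |
|---|---|---|---|
| POW1 | 6 to 8 | 6 | 8 + 5 + 1 = 14 |
| POW2 | 12 to 16 | 12 | 16 + 5 + 1 = 22 |
| POW3 | 18 to 24 | 18 | 24 + 5 + 1 = 30 |
| POW4 | 23 to 33 | 23 | 33 + 5 + 1 = 39 |
| POW8 | 51 to 61 | 51 | 61 + 5 + 1 = 67 |

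The minimum is 6 days, or 6 × 24 = 144 hours. The maximum of 67 days applies to detection in the Surveillance Phase, the only phase from which Section 7.3.3 routes patients to Mavyret. NAT testing continues after POW8, so a later detection would give an older result.

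Section 2.1 expects early viremia, and Section 6.2 allows for a start during the transplant admission. The POW1 to POW2 range of 6 to 22 days is therefore the more likely one.

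**How many women would be tested**
- Treated patients: Section 10.5 expects about 70% to be treated. The protocol gives the sample size as 10 (Protocol Summary, Section 10.5) and as 20 (Sections 5.4 and 5.6). So 0.70 × 10 = 7, or 0.70 × 20 = 14.
- The documents do not give the share who are women of childbearing potential. I assume 5% to 20% of treated patients.
- N = 10: 7 × 0.05 = 0.35 to 7 × 0.20 = 1.4.
- N = 20: 14 × 0.05 = 0.7 to 14 × 0.20 = 2.8.

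These are women who would take the added test, not pregnancies missed.

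**The case against.** **The rule is already met.** If the study intervention is the transplant, or the surveillance that follows it directly, then the enrolment test falls within 24 hours and its result precedes any Mavyret dose. The 24-hour wording is also qualified as what is usual. This stands, and it is why the point is a gap rather than a contradiction. For the same reason, 144 hours against 24 is a comparison and not a breach of a limit. But on this reading the protocol sets no maximum age for the result when the study product is first given.

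**Standard-of-care testing may fill the gap.** Section 7.2.1 classes the test as standard of care. The Section 20 table is an incomplete record of such tests: HBV and HIV tests are in the Section 7.3.3 text at POW4 and PMW4 but not in those table columns. A newer result may therefore exist in practice, and the documents cannot rule it out. For the pregnancy test, however, text and table agree that only enrolment is scheduled. Other standard-of-care tests, such as hematology and biochemistry, are listed visit by visit.

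**The risk is low.** Section 5.1 requires birth control under the mycophenolate REMS and a barrier method, Section 7.1.1 takes a medication history covering hormonal contraceptives, and the patient has just had a heart transplant. This stands as to likelihood. None of it establishes pregnancy status. Section 7.5 also prohibits oral contraceptives containing ethinyl estradiol, so some women may have to change method around treatment.

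**A positive result has no set consequence.** Section 8.4.4 plans counselling rather than a dosing rule, and Section 5.7.2 warns that stopping Mavyret risks acute or chronic HCV. The gain is thus in timing: the woman could weigh the choice before the first dose.

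**Conclusion.** The concern holds as a cheap improvement. No pregnancy test is scheduled between Day 0 and the first Mavyret dose. For a site that follows the schedule and does no unscheduled test, the result would be 6 to 67 days old at first dose, most likely 6 to 22 days. These ages assume detection at a scheduled surveillance NAT, a same-day result and a start within 5 days.

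On the assumed 5% to 20% share, the added test would reach about 0.4 to 2.8 women across the two stated sample sizes. The effect on the trial as a whole is small and there is none on its primary analysis. The case for the change rests on patient safety and very low cost.

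**What to change.** 1. In Section 7.3.3, add to the PMW0 entry a urine pregnancy test for women of childbearing potential, with the result available before the first Mavyret dose.
2. Mark the test in the PMW0 column of the Section 20 table.
3. State in Section 7.2.1 that the enrolment test precedes the transplant and the PMW0 test precedes Mavyret.

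With this change the result would be at most about 24 hours old at first dose if the test is done within a day of it.

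The cost is one urine test per treated woman of childbearing potential, at a visit already held in person. The 5-day window at PMW0 leaves room for it, so treatment need not be delayed. The edits need IRB approval as an amendment (Section 13.2). If the test is counted as study-specific rather than standard of care, it must also be added to the limited list in Section 15.1.
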